**Table 2:** **Study Endpoints**

Endpoint	Name	Description	Time frame
Secondary	Proportion of subjects with serological protection against tetanus toxoid	Subjects with serological protection have: Anti-tetanus toxoid IgG concentration $\geq 0.1$ IU/mL	At the Day 28 post-vaccination visit
	Proportion of subjects with serologic response to at least 5 of the following pneumococcal serotypes: 3, 6B, 9N, 11A, 14, 19A, 19F, 22F and 23F	Serologic response to PPSV23: The proportion of subjects with a $\geq 2$ -fold increase in anti-pneumococcal polysaccharide vaccine titer in $\geq 5$ of the indicated serotypes	At the Day 28 post-vaccination visit
	Proportion of subjects with serological protection against the following pneumococcal serotypes: 3, 6B, 9N, 11A, 14, 19A, 19F, 22F and 23F	Subjects with serological protection have: Anti-pneumococcal polysaccharide IgG concentration $\geq 1.3$ $\mu$ g/mL for indicated serotypes	At the Day 28 post-vaccination visit
	Safety of concomitant vaccine administration in subjects taking ozanimod	(S)AE incidence, severity, causality, type Change from baseline in clinical lab values and incidence of abnormal lab values Listing of subjects with Investigator-confirmed relapses	Over the study

**Table 2:** **Study Endpoints**

Endpoint	Name	Description	Time frame
Exploratory	Proportion of subjects with serologic response to the seasonal influenza vaccine	Subjects with serologic response have: At least a four-fold titer increase in titer if the pre-vaccination titer $\geq 1:10$ , or an increase hemagglutination titer $\geq 1:40$ in subjects with a pre-vaccination titer $< 1:10$ . To be calculated separately for each antigen/strain, and combined (ie, for proportions of subjects who meet responder criteria for at least one antigen)	At the Day 28 post-vaccination visit
	Proportion of subjects with serological protection against seasonal influenza	Subjects with serological protection have: Hemagglutination inhibition antibody titers $\geq 1:40$ To be calculated separately for each antigen/strain, and combined (ie, for the proportion of subjects who have serological protection against at least one influenza strain)	At the Day 28 post-vaccination visit

**Table 2:** **Study Endpoints**

Endpoint	Name	Description	Time frame
	Geometric Mean Titer (GMT) ratio of anti-influenza antibodies	The ratio of the geometric mean of the post-vaccination anti-hemagglutination inhibition titer (at the post vaccination day 28 visit) divided by the geometric mean of the pre-vaccination anti-hemagglutination inhibition titer To be calculated separately for each antigen/strain.	At the Day 28 post-vaccination visit
	Assessment if at least one of the specified criteria is met for each treatment arm for each influenza strain	For each treatment arm, at least one criterion is met for each strain: Number of subjects with serologic response > 40% The ratio of geometric mean post vaccination antibodies titers compared to pre-vaccination is $\geq 2.5$ The proportion of subjects achieving a hemagglutinin titer $\geq 40$ is $> 70\%$	At the Day 28 post-vaccination visit

**Table 2:** **Study Endpoints**

Endpoint	Name	Description	Time frame
	GMC ratio of anti-tetanus toxoid IgG	The ratio of the geometric mean of the post-vaccination anti-tetanus toxoid IgG concentration (at the post vaccination day 28 visit) divided by the geometric mean of the pre-vaccination anti-tetanus toxoid IgG concentration	At the Day 28 post-vaccination visit
	GMC ratio of anti-tetanus toxoid IgM	The ratio of the geometric mean of the post-vaccination anti-tetanus toxoid IgM concentration (at the post vaccination day 28 visit) divided by the geometric mean of the pre-vaccination anti-tetanus toxoid IgM concentration	At the Day 28 post-vaccination visit
	GMC ratio of anti-pneumococcus IgG for each pneumococcal serotype in PPSV23	The ratio of the geometric mean of the post-vaccination anti-pneumococcus IgG concentration (at the post vaccination day 28 visit) divided by the geometric mean of the pre-vaccination anti-pneumococcus IgG concentration. To be calculated separately for each pneumococcal serotype.	At the Day 28 post-vaccination visit

**Table 2:** **Study Endpoints**

Endpoint	Name	Description	Time frame
	GMC ratio of anti-pneumococcus IgM for each pneumococcal serotype in PPSV23	The ratio of the geometric mean of the post-vaccination anti-pneumococcus IgM concentration (at the post vaccination day 28 visit) divided by the geometric mean of the pre-vaccination anti-pneumococcus IgM concentration.	At the Day 28 post-vaccination visit
	Proportion of subjects with serologic response to reduced diphtheria toxoid	Serologic response to diphtheria toxoid: If pre-vaccination antibody titer is $\leq 0.10$ IU/mL, post-vaccination level $\geq 0.40$ IU/mL; if pre-vaccination antibody titer is $> 0.10$ IU/mL and $\leq 2.56$ IU/mL, at least a four-fold rise in titer; if pre-vaccination IgG concentration is $> 2.56$ IU/mL, at least a two-fold increase in titer	At the Day 28 post-vaccination visit
	Proportion of subjects with serological protection against reduced diphtheria toxoid	Subjects with serological protection have: Anti-diphtheria toxoid IgG concentration $\geq 0.1$ IU/mL	At the Day 28 post-vaccination visit

**Table 2:** **Study Endpoints**

Endpoint	Name	Description	Time frame
	GMC ratio of anti-diphtheria toxoid IgG	The ratio of the geometric mean of the post-vaccination anti-diphtheria toxoid IgG concentration (at the post vaccination day 28 visit) divided by the geometric mean of the pre-vaccination anti-diphtheria toxoid IgG concentration	At the Day 28 post-vaccination visit
	GMC ratio of anti-diphtheria toxoid IgM	The ratio of the geometric mean of the post-vaccination anti-diphtheria toxoid IgM concentration (at the post vaccination day 28 visit) divided by the geometric mean of the pre-vaccination anti-diphtheria toxoid IgM concentration	At the Day 28 post-vaccination visit

**Table 2:** **Study Endpoints**

Endpoint	Name	Description	Time frame
	Proportion of subjects with serologic response to pertussis	Serologic response: In initially seronegative subjects (< 5 EL.U/mL), post-vaccination level $\geq$ 20 EL.U/mL; if pre-vaccination antibody titer $\geq$ 5 EL.U/mL and < 20 EL.U/mL, at least a 4-fold increase in titer; if pre-vaccination antibody titer $\geq$ 20 EL.U/mL, at least a 2-fold in titer To be calculated separately for each pertussis antigen	At the Day 28 post-vaccination visit
	Proportion of subjects with serological protection against pertussis	Subjects with serological protection have: Anti-pertussis antigen IgG concentration $\geq$ 5 EL.U/mL To be calculated separately for each pertussis antigen	At the Day 28 post-vaccination visit

**Table 2:** **Study Endpoints**

Endpoint	Name	Description	Time frame
	GMC ratio of anti-pertussis IgG	The ratio of the geometric mean of the post-vaccination anti-pertussis antigen IgG concentration (at the post vaccination day 28 visit) divided by the geometric mean of the pre-vaccination anti-pertussis antigen IgG concentration. To be calculated separately for each pertussis antigen	At the Day 28 post-vaccination visit
	GMC ratio of anti-pertussis IgM	The ratio of the geometric mean of the post-vaccination anti-pertussis antigen IgM concentration (at the post vaccination day 28 visit) divided by the geometric mean of the pre-vaccination anti-pertussis antigen IgM concentration To be calculated separately for each antigen	At the Day 28 post-vaccination visit
	PK	Plasma concentrations of ozanimod and its metabolites (ie, CC112273)	At baseline and end of study
	PD and Plasma biomarker analysis	Cytokines, chemokines, inflammatory markers, and COVID-19 antibodies	At baseline and end of study

### **3           OVERALL STUDY DESIGN**

#### **3.1       Study Design**

The proposed study is a Phase 3b, multicenter, open-label, study to evaluate the immunological response to, and the safety of, vaccines in subjects with RMS who receive oral ozanimod 0.92 mg, non-pegylated IFN- $\beta$ , or no DMT. The overall study design is presented in [Figure 1](#). The schedule of events is presented in [Table 3](#).

[figure not shown]
The study will include two cohorts differentiated by the vaccines administered. Cohort 1 comprises subjects who receive Tdap, PPSV23, and the seasonal inactivated influenza vaccine. Cohort 2 comprises subjects who have already received the seasonal influenza vaccine. As a result, Cohort 2 subjects will receive Tdap and PPSV23, only. Initiation of Cohort 2 will be based on the availability of eligible subjects who have not previously been vaccinated with the seasonal inactivated influenza vaccine. Subjects who meet all eligibility criteria but have already received the influenza vaccine as described in Exclusion Criterion #13, will be enrolled in Cohort 2. Subjects who meet all eligibility criteria, including Exclusion Criterion #13, will continue to be enrolled in Cohort 1 throughout the time both cohorts are open for enrollment. Cohort 2 may be opened for enrollment at any time determined by the Sponsor, but is estimated to occur after no less than 60% of subjects of the planned of the planned total enrollment have been recruited into Cohort 1.

No greater than 25% of subjects in either treatment arm who discontinued an S1P modulator due to S1P modulator-associated lymphopenia will be enrolled who have an ALC  $<0.5 \times 10^9/L$ . This threshold corresponds to approximately the 25th of ALCs mean levels observed in the ozanimod pivotal trials.

[figure not shown]
The study will be conducted in compliance with the International Council on Harmonisation (ICH) of Technical Requirements for Registration of Pharmaceuticals for Human Use/Good Clinical Practice (GCP) and applicable regulatory requirements.

**Figure 1: Overall Study Design**

**Cohort 1:**

**Cohort 2:**

Abbreviations: Tdap = Tetanus, diphtheria, and acellular pertussis vaccine; PPSV23 = Pneumococcal polysaccharide vaccine; IFN = Interferon; DMT = Disease modifying therapy.

## **Screening Period**

Subjects who have signed the informed consent form (ICF) will undergo screening evaluations to determine eligibility. The screening period may last from -14 to Day 1 (Baseline). Eligible subjects can enter the active treatment/vaccination period.

The Screening requirements can be performed on the same day as Day 1, provided that all Screening requirements are completed before any Day 1 assessments and vaccine administration is performed. In this case, Day 1 assessments that are also conducted as Screening assessments do not have to be duplicated, including pregnancy screening.

Because the vaccines administered in this study are approved vaccines, they do not require laboratory testing prior to administration and are typically administered on the same day without a prior monitoring period in a broad range of the general population. Conducting Screening and Day 1 assessments on the same day is considered acceptable.

## **Active Treatment/Vaccination Period**

At the Day 1 Visit, eligible subjects in Cohort 1 will have pre-vaccination blood samples collected (for titer determination), followed by administration of the following three vaccines:

- Tdap booster vaccine
- PPSV23
- Seasonal influenza vaccine

At the Day 1 Visit, eligible subjects in Cohort 2 will have pre-vaccination blood samples collected (for titer determination), followed by administration of the following two vaccines:

- Tdap booster vaccine
- PPSV23

The vaccines administered in this study are commercially available and approved in the jurisdictions of the clinical sites, and administration will occur in accordance with the drug label. After Day 1, the post-treatment follow-up period starts.

## **Post-Treatment Follow Up Period**

The post treatment follow-up period spans 28 days, with one visit at post-vaccination Day 28, during which subjects will return to the site to have blood samples collected (for serological determinations) and adverse events (AE) recorded. Upon completion of the Day 28 Visit, subjects have completed the study.

## **Relapse Assessments**

Subjects who experience worsening neurological symptoms during the study should contact the Investigator and describe their symptoms, ideally within 48 hours of symptom onset. The Investigator will also inquire about worsening neurological symptoms at the Day 28 Visit. If, in the opinion of the Investigator, the worsening neurological symptoms are potentially due to an MS relapse, a relapse visit should be scheduled within 7 days of site contact. The following manifestations are considered consistent with an MS relapse: monophasic clinical episode with

subject-reported neurologic symptoms and objective findings typical of multiple sclerosis, reflecting a focal or multifocal inflammatory demyelinating event in the CNS, developing acutely or sub acutely, with a duration of at least 24 hours, with or without recovery, and in the absence of fever or infection ([Thompson, 2018](#)). The relapse visit can take place at the same day as the Day 28 Visit.

### **3.2 Study Duration for Subjects**

This study will include a screening period of up to 14 days. The study period is from Day 1 Vaccination to the 28-day assessment visit. The maximum potential length from screening to end of trial 45 days. Screening and Day 1 may occur on the same day in eligible subjects.

### **3.3 End of Trial**

The End of Trial is defined as either the date of the last visit of the last subject to complete the post-treatment follow-up, or the date of receipt of the last data point from the last subject that is required for primary, secondary and/or exploratory analyses, as prespecified in the protocol, whichever is the later date.

## **4 STUDY POPULATION**

### **4.1 Number of Subjects**

Approximately 60 subjects with relapsing forms of MS will be enrolled; approximately 30 of these subjects will be taking ozanimod for at least █ days prior to the Day 1 Visit, and approximately 30 subjects will be taking non-pegylated IFN- $\beta$  or not receiving any DMT.

### **4.2 Inclusion Criteria for All Subjects**

Subjects must satisfy the following criteria to be enrolled in the study:

1. Male or female subjects 18 to 65 years of age, inclusive, at the time of signing the ICF.
2. Subject must understand and voluntarily sign an ICF prior to any study-related assessments/procedures being conducted.
3. Subject is willing and able to adhere to the study visit schedule and other protocol requirements.
4. Subject has a diagnosis of MS according to the 2017 revision of the McDonald diagnostic criteria and has RMS: RRMS or secondary progressive MS with active disease based on recent clinical relapse or MRI lesion activity ([Thompson, 2018](#))
5. At Screening, subjects must be on one of the following three treatment options and willing to remain on the same treatment for the duration of the study:
  - a. Treatment with ozanimod (0.92 mg maintenance dose). Ozanimod treatment must have been initiated at least █ days prior to the Day 1 Visit. Subjects should be compliant with the ozanimod label. In addition, in the █ days prior to Day 1, ozanimod treatment must not have been interrupted for more than 1 day.
  - b. Treatment with a non-pegylated form of IFN- $\beta$  and compliant with dosing within █ of Day 1 per the manufacturer's label
  - c. No treatment with a DMT for RMS
6. Subject is ambulatory (with or without walking aid) at Screening.
7. Subject is relapse-free in the 30 days prior to Day 1; during this period, subjects must have been clinically stable, without systemic corticosteroid or adrenocorticotropic hormone treatment.
8. Subjects who receive ozanimod or non-pegylated IFN- $\beta$  as their standard of care medication must do so in accordance with the local drug label.
9. Females of childbearing potential (FCBP) who receive ozanimod as their standard of care medication must agree to use contraception according to the approved local label.

All Subjects:

Periodic abstinence (calendar, symptothermal, post-ovulation methods), withdrawal (coitus interruptus), spermicides only, and lactational amenorrhoea method (LAM) are not acceptable methods of contraception. Female condom and male condom should not be used together.

### **4.3 Exclusion Criteria for Cohort 1**

The presence of any of the following will exclude a subject from enrollment:

1. Subject is pregnant, lactating, or has a positive urine  $\beta$ -subunit of human chorionic gonadotropin ( $\beta$ -hCG) measured during screening or on Day 1
2. Subject has any infections, including:
  - a. Infection requiring hospitalization or treatment with intravenous (IV) antibiotics, antivirals, antifungal medication, anti-parasite medication within 30 days prior to Day 1
  - b. Infection requiring treatment with oral antibiotics, antivirals, antifungal medication, anti-parasite medication within 14 days prior to Day 1
  - c. Fever  $\geq 40^{\circ}\text{C}$  within 14 days of enrollment
  - d. SARS-CoV-2 infection with symptoms that have not completely resolved, and based on Investigator assessment in consultation with the Clinical Trial Physician/Medical Monitor, there are no sequelae that would place the participant at a higher risk of receiving investigational treatment.
  - e. Any ongoing infection at Day 1
3. Subject has history of cancer, including solid tumors and hematological except for basal cell cancer of the skin and carcinoma in situ of the cervix, which are exclusionary if they have not been excised and resolved
4. Subject has a BMI  $\geq 35 \text{ kg/m}^2$
5. Subject has known contraindication against Tdap, PPSV23, or quadrivalent seasonal influenza vaccine (Cohort 1 only), including, but not limited to:
  - a. a history of anaphylactic/anaphylactoid or severe allergic reaction to any component of the vaccines, including egg as contained in the influenza vaccine, or a history of an Arthus-type hypersensitivity reaction against tetanus or diphtheria toxoid containing vaccines
  - b. Encephalopathy or neurological complication following prior vaccinations containing pertussis antigens
  - c. Thrombocytopenia following prior vaccination against tetanus, diphtheria, or pertussis
6. Subject has a history of or currently active primary or secondary immunodeficiency
7. Subjects has a history of Guillain-Barré Syndrome
8. Subject has severely compromised cardiac or pulmonary function for which a systemic hypersensitivity reaction to any of the vaccines would pose a significant risk
9. Subject has any moderate or severe acute illness, as assessed by the investigator
10. Subject has a history of alcohol abuse or drug abuse within 1 year prior to Screening
11. Subject has received any vaccine within 30 days prior to Day 1 including any SARS-CoV-2 (COVID-19) vaccine (first or second dose), or planned vaccines including COVID vaccine throughout the study period.
12. Subject has received any tetanus vaccine within 1 year prior to Screening.
13. Subject has received the seasonal influenza vaccine for the 2021/2022 influenza season prior to Day 1, or history of influenza vaccine for the 2020/2021 influenza season within 6 months prior to Day 1.

14. Subject has received PPSV23 within 5 years prior or PCV13 within 1 year of the Day 1.
15. For subjects receiving ozanimod: known contraindication against receiving ozanimod, according to product label.
16. For subjects on IFN- $\beta$ : known contraindication against IFN- $\beta$  or ongoing tolerability issues that might jeopardize compliance during the study (eg, injection site reactions requiring treatment, intolerable influenza-like symptoms, etc).
17. Subject has previous treatment with one of the following medications or interventions within the corresponding timeframe described as follows:
  - a. Previous treatment with lymphocyte-depleting therapies (eg, Campath®, anti-CD4, cladribine, cyclophosphamide, mitoxantrone, total body irradiation, bone marrow transplantation, stem cell transplantation, alemtuzumab, or daclizumab)
  - b. Previous treatment with teriflunomide within 8 months prior to randomization (unless teriflunomide plasma concentration is less than 0.02 mg/L [20 ng/mL]) or the subject had successfully followed the accelerated elimination procedure as described in the product label.
  - c. 180 Days prior to Day 1 or 5 half-lives, whichever is longer: any investigational agent or interventional therapy (excluding life-style interventions)
  - d. 180 Days prior to Day 1: azathioprine, methotrexate, cyclosporine, mycophenolate anti-CD20 mAbs (including rituximab, ocrelizumab, ofatumumab), Bruton's tyrosine kinase (BTK) inhibitors. After discontinuation of anti-CD20 mAbs, subjects must have documentation of ALC and gamma globulin levels within the normal range.
  - e. 60 Days prior to Day 1: fingolimod, dimethyl fumarate
  - f. Subjects who discontinued an S1P modulator due to lymphopenia must have a documented ALC  $>0.2 \times 10^9/L$  within 6 months prior to baseline and for subjects on ozanimod, documented after a minimum of [redacted] days of treatment with ozanimod.
  - g. 30 Days prior to Day 1: Systemic corticosteroids or adrenocorticotrophic hormone (ACTH).
  - h. 14 Days prior to Day 1: Pegylated IFN $\beta$ -1a, glatiramer acetate, siponimod
  - i. Planned start of IFN- $\beta$  or other MS disease modifying therapy after Day 1 throughout the study period.
  - j. Use of anti-pyretic treatments, including acetaminophen, aspirin, and other non-steroidal anti-inflammatory drugs (NSAIDs), for a period of 24 hours prior to administration of the vaccine and for a minimum of 6 hours after.
  - k. Any systemic immunosuppressive treatments with potential overlapping effects with the baseline of this study. Corticosteroids that are by non-systemic routes (eg, topical, inhaled, intra-articular) are allowed.
18. History of treatment with IV immunoglobulin (IVIg) or plasmapheresis within 4 weeks prior to Day 1.
19. Any significant medical condition, laboratory abnormality, or psychiatric illness that places the subject at unacceptable risk if he/she were to participate in the study in the opinion of the investigator.
20. Any condition that confounds the ability to interpret data from the study.

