### **1.3.6      *Rationale for Selected Endpoints***

#### **Primary Endpoint**

**Tetanus Toxoid Immune Response** - The proportion of subjects with serologic response to tetanus toxoid in the Tdap vaccine will serve as the primary endpoint in this study. Serologic response to tetanus toxoid is measured by comparing the anti-tetanus toxoid IgG antibody titers at 4 weeks post-vaccination compared to the pre-vaccination titers. The antibody titers will be measured by an ELISA method. Subjects with a pre-vaccination IgG antibody titer level  $\leq 0.10$  IU/mL will have a serologic response if post-vaccination titer levels are  $\geq 0.40$  IU/mL. To demonstrate a serologic response if pre-vaccination titer levels are  $> 0.10$  IU/mL and  $\leq 2.7$  IU/mL, subjects will have at least a 4-fold increase in post-vaccination titers. If subjects have a pre-vaccination titer level  $> 2.7$  IU/mL, they will have at least a 2-fold increase in titers to demonstrate a response. This endpoint is supported by the recommendations to manufacturers of tetanus vaccines to establish immune response which stipulates 0.10 IU/mL as a seroprotective level against tetanus and establishes increased Ab titers needed to demonstrate immune response based on pre-vaccination titer level ([WHO Technical Report Series, No. 980, Annex 5](#)). The requirement for a serologic response above the upper baseline level of 2.7 IU/mL as a 2-fold increase is supported by the WHO recommendations to establish tetanus vaccine efficacy, as well as by research demonstrating subjects with higher baseline titers are associated with less than a 4-fold response to vaccination ([Petras, 2018](#); [Halperin, 2018](#)). Assessing the tetanus toxoid vaccine immune response at 4 weeks is also recommended by the [WHO Technical Report Series, No. 980, Annex 5](#) and coincides with peak humoral immune response in adults ([Blatter, 2009](#)).

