#### **Secondary Endpoints**

**Tetanus Toxoid Immune Response** – The proportion of subjects with anti-tetanus toxoid IgG  $\geq 0.1$  indicative of seroprotection.

**Pneumococcal PPSV23**- The proportion of subjects with a serologic response and serological protection to PPSV23 will be assessed in this study. Serologic response to PPSV23 is demonstrated by comparing the IgG antibody titers at 4 weeks post vaccination to the pre-vaccination concentration. The antibody titers will be measured by an ELISA method. Of the 23 serotypes contained in PPSV23, there is a subset associated with increased risk of invasive and/or severe

disease, including death: Serotypes 3, 6B, 9N, 11A, 14, 19A, 19F, 22F and 23F (Sjöström, 2006; Weinberger, 2010). These subtypes will be assessed in this study for pneumococcal vaccination immune response. The proportion of subjects with at least a 2-fold increase in post-vaccination anti-pneumococcal polysaccharide IgG titers in at least 5 of these serotypes will constitute the primary analysis for serologic response to PPSV23. Serologic response will also be determined separately for all selected serotypes. Additional secondary endpoints to assess PPSV23 vaccine response are the proportion of subjects with anti-pneumococcal polysaccharide IgG concentration  $\geq 1.3 \text{ } \mu\text{g/mL}$  for the selected serotypes indicative of seroprotection. The increase in antibody polysaccharide vaccine criteria (ie, 2-fold increase) is substantiated by studies that show most subjects with a pre-vaccination titer of  $\geq 1.3 \text{ mg/mL}$  can mount a 2-fold increase in titer on immunization but only a minority of subjects with high initial titers will be capable of mounting a 4-fold increase in antibody titers after vaccination (Orange, 2012; LaFon, 2018). A normal response to vaccination in unprotected subjects has been defined as conversion to a protected concentration ( $1.3 \text{ } \mu\text{g/mL}$ ) with a 2-fold rise in antibody concentration in at least 70% of serotypes tested (Orange, 2012; LaFon, 2018). In addition, in a study comparing anti-pneumococcal vaccine antibody titers from the same specimens tested across multiple reference laboratories, the results for algorithms using a 2-fold cutoff were consistent between laboratories but a 4-fold increase criteria led to disparity across labs with low concordance (Daly, 2015).

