**Table 2:** **Study Endpoints**

Endpoint	Name	Description	Time frame
Primary	Proportion of subjects with serologic response to tetanus toxoid	Serologic response to tetanus toxoid:  If pre-vaccination antibody titer is $\leq 0.10$ IU/mL, post-vaccination level $\geq 0.40$ IU/mL; if pre-vaccination antibody titer is $> 0.10$ IU/mL and $\leq 2.7$ IU/mL, at least a 4-fold increase in titer; if pre-vaccination antibody titer is $> 2.7$ IU/mL, at least a 2-fold increase in titer	At the Day 28 post-vaccination visit

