### **8.1      Prohibited Concomitant Medications and Procedures**

**The following medications cannot be used during the trial through the End of Treatment Visit:**

- Any medications prohibited by the product labels of country for ozanimod and IFN- $\beta$  compounds
- Any approved and unapproved disease-modifying MS agents, excluding ozanimod and IFN- $\beta$
- Treatment with Class Ia or Class III anti-arrhythmics (examples of prohibited systemic cardiac medications are provided in [Table 6](#) ) or treatment with a combination of 2 or more agents known to prolong PR interval (eg, combination of a beta blocker and verapamil) are prohibited during the study unless approved by the Sponsor's representative. Note that [Table 6](#) does not provide a comprehensive list. The Medical Monitor should be contacted for further guidance if needed.
- Systemic corticosteroid therapy or ACTH, except for treatment of protocol-defined treatment of relapses. Corticosteroids that are by non-systemic routes (eg, topical, inhaled, intra-articular) are allowed.
- Any vaccine, including first or second dose of COVID-19 vaccine
- Intravenous immunoglobulin (IVIg) or plasmapheresis
- Immunosuppressive agents known to deplete lymphocytes
- Breast cancer resistance protein inhibitors (eg, cyclosporine, eltrombopag)
- Monoamine oxidase inhibitors (eg, selegiline, phenelzine)
- CYP2C8 inhibitors (eg, gemfibrozil and clopidogrel) or inducers (eg, rifampicin)

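### A 4-week IVIg washout can leave donor IgG in the Day 1 sample that the IgG response endpoints are judged against; probably rare, and cheap to close

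*Combined protocol and SAP*

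**What the plan says.** Section 4.3, criterion 18, excludes subjects with a "History of treatment with IV immunoglobulin (IVIg) or plasmapheresis within 4 weeks prior to Day 1". Section 4.4 applies the same rule to Cohort 2, which drops only criterion 13. Section 8.1 lists "Intravenous immunoglobulin (IVIg) or plasmapheresis" among the treatments barred during the trial, so only infusions before the study matter. No reason is given for 4 weeks.

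The primary endpoint in Table 2 is the "Proportion of subjects with serologic response to tetanus toxoid". Section 1.3.6 says it is "measured by comparing the anti-tetanus toxoid IgG antibody titers at 4 weeks post-vaccination compared to the pre-vaccination titers". The rule depends on the Day 1 level:

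- at or below 0.10 IU/mL, the Day 28 level must reach 0.40 IU/mL;
- above 0.10 and up to 2.7 IU/mL, "subjects will have at least a 4-fold increase in post-vaccination titers";
- above 2.7 IU/mL, "they will have at least a 2-fold increase in titers to demonstrate a response".

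Diphtheria and pertussis have tiers of the same kind. Pneumococcal response is "at least a 2-fold increase in post-vaccination anti-pneumococcal polysaccharide IgG titers in at least 5 of these serotypes", out of nine. The IgG GMC ratios also divide Day 28 by Day 1.

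On recording, Section 8 collects treatments and blood products from 30 days before Day 1. The Section 6.1 medication review names a 30-day period before screening, with an exception for disease treatments. The per-protocol definition in Section 9.2 and the model factors named in Section 9.6 mention neither immunoglobulin exposure nor baseline titre.

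**The concern.** IVIg is taken here to be pooled donor IgG that carries the specificities this trial measures. Donor antibody still circulating on Day 1 is counted in the pre-vaccination level, although it is not the subject's own. Part of it is gone by Day 28. The denominator of the fold-rise is too large, and the Day 1 reading can place the subject in the wrong tier.

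An exposed subject would then be scored partly on donor antibody, in the primary endpoint and in the other IgG fold-rise and IgG GMC-ratio endpoints. An infusion 5 or 6 weeks before Day 1 breaks no rule, so the subject stays in the per-protocol set. If it was given for something other than MS, it may not be recorded either, and the error could not then be found afterwards.

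**Working it through.** **The plan's own precision figure (Section 9.3).** With n = 30 and a response rate of 0.45, 1.96 × √(0.45 × 0.55 / 30) = 0.178. Averaged over the Binomial(30, 0.45) distribution, the expected half-width is 0.175, as stated. The 2.5% and 97.5% quantiles are 8/30 = 0.267 and 19/30 = 0.633, also as stated. One subject is 1/30 = 3.3 points.

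**Assumptions, because the documents give no figure.** IgG half-life (HL) 21 to 28 days; donor tetanus IgG on Day 1 of 0.2 to 0.5 IU/mL in the examples; number of exposed subjects unknown.

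**Donor IgG left on Day 1**, 0.5^(days since infusion / HL):

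| Days since infusion | HL 21 | HL 28 |
|---|---|---|
| 28 (limit allowed) | 40% | 50% |
| 56 | 16% | 25% |
| 5 half-lives (105 or 140) | 3.1% | 3.1% |
| 180 | 0.3% | 1.2% |

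At HL 7 days only 6% would be left after 28 days.

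**Observed fold-rise.** Let d = 0.5^(27/HL) be the share of the Day 1 donor IgG still present on Day 28: 0.410 at HL 21 and 0.513 at HL 28. Observed fold = (own post + donor × d) / (own pre + donor).

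| Own IgG, IU/mL | Donor on Day 1 | Observed | Fold | True / scored |
|---|---|---|---|---|
| 0.5 → 2.5 (5-fold) | 0.2 | 0.70 → 2.58–2.60 | 3.7 | responder / non-responder |
| 0.5 → 2.5 (5-fold) | 0.5 | 1.00 → 2.71–2.76 | 2.7–2.8 | responder / non-responder |
| 0.05 → 0.65 | 0.2 | 0.25 → 0.73–0.75 | 2.9–3.0 | responder / non-responder (now in the 4-fold tier) |
| 0.5 → 5.0 (10-fold) | 0.2 | 0.70 → 5.08–5.10 | 7.3 | responder / responder |
| 0.5 → 5.0 (10-fold) | 0.5 | 1.00 → 5.21–5.26 | 5.2–5.3 | responder / responder |
| 2.5 → 7.5 (3-fold) | 0.5 | 3.00 → 7.71–7.76 | 2.6 | non-responder / responder (now in the 2-fold tier) |

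**True rise needed.** With r = donor / own level on Day 1, a subject in the tetanus 4-fold tier needs a true rise of 4 + r(4 − d), and each pneumococcal serotype needs 2 + r(2 − d). At HL 21, for r = 0.1, 0.25, 0.5 and 1, tetanus needs 4.4, 4.9, 5.8 and 7.6, and pneumococcus 2.2, 2.4, 2.8 and 3.6. HL 28 changes these by at most 0.1. Decay is not essential: with d = 1 the tetanus requirement is still 4 + 3r.

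**Seroprotection.** Donor IgG of 0.25 IU/mL on Day 1 leaves 0.25 × 0.410 = 0.103 to 0.25 × 0.513 = 0.128 IU/mL on Day 28, which alone clears the 0.1 IU/mL threshold.

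**Size at arm level.** In a simulation (own Day 1 titre lognormal, geometric mean 1 IU/mL, log SD 1; fold-rise lognormal, log SD 0.9, set to a true rate of 45%; HL 21; donor 0.25 to 1 IU/mL), 23% to 47% of true responders among exposed subjects were lost and 1% to 4% of non-responders gained. Their observed rate was 35.3% to 26.2%. If 10% of an arm were exposed, the expected shift would be 0.10 × (45 − 35.3) = 1.0 to 0.10 × (45 − 26.2) = 1.9 points; at 5% exposed, half that. For the IgG GMC ratio, one subject in 30 reading 3.69 instead of 5 multiplies the arm's ratio by (3.69/5)^(1/30) = 0.990.

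**The case against.** The strongest reply is that no effect on the trial has been shown. Half-life, donor content and the number exposed all come from outside the documents. Criteria 6 and 7 exclude immunodeficiency and Guillain-Barré Syndrome. Criterion 17d asks for normal gamma globulin after anti-CD20 therapy. Criterion 18 together with the in-study ban rules out roughly monthly maintenance IVIg. Criterion 20 lets the investigator exclude anything that confounds interpretation. The study tests no hypothesis, and Section 9.6 already urges caution about differences between arms. All of this stands as a reason to expect few exposed subjects. It does not close the gap: criterion 20 is discretionary and names no product or period, and nothing else reaches a completed course that ended 5 weeks before Day 1.

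A reader might also infer more than the documents support:

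- *That every fold-rise or GMC endpoint is affected.* Table 2 has separate IgM GMC ratios, which pooled IgG does not touch.
- *That the bias always runs toward non-response.* The looser tier above 2.7 IU/mL can reverse it.
- *That 40% to 50% contamination is typical.* It is the limit case, and it falls to 16% to 25% at 56 days.
- *That criterion 17c makes criterion 18 inconsistent.* The rule "180 Days prior to Day 1 or 5 half-lives, whichever is longer: any investigational agent" is a generic one for investigational agents. The plan sets other windows agent by agent, and nothing makes 17c the benchmark for IVIg.
- *That the comparison of arms is biased.* This needs unequal exposure, which is possible without randomization but is not shown.

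**Conclusion.** The point holds as a limited measurement weakness. Criterion 18 admits subjects whose Day 1 IgG may include donor antibody, and the IgG endpoints have no protection against it. True responders near a threshold can be scored as non-responders; the opposite error is possible near 2.7 IU/mL, and Day 28 seroprotection can be overstated. Clear responders, such as the 10-fold risers above, keep their classification.

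The conclusion assumes an IgG half-life of 21 to 28 days and donor titres that are not small beside the subject's own. At a 7-day half-life it would matter little unless the dose were large. The number exposed is unknown and probably small. One, two or three misclassified subjects shift an arm by 3.3, 6.7 or 10 points, against a half-width of about 17.5. This justifies an inexpensive correction. It does not threaten the study.

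**What to change.** 1. Lengthen the immunoglobulin part of criterion 18 to about 5 IgG half-lives before Day 1: 105 to 140 days under the stated assumption. A flat 180 days is a simple conservative choice; adding a half-life alternative to it would have no effect under that assumption. Cover any immunoglobulin product: intravenous, subcutaneous or specific, such as tetanus immune globulin.
2. Ask about immunoglobulin history over the same window at screening and record it on the CRF. Without this, the 30-day recording period makes the longer window unenforceable.
3. For subjects already enrolled with such exposure, state in the statistical analysis plan, before the Day 28 results are examined, that they are either excluded from the per-protocol IgG analyses or removed in a sensitivity analysis, and list them. IgM analyses can keep them.

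The cost is a few extra screen failures, in a study that has already reported enrollment challenges; one added history question, to be put to enrolled subjects as well; and slightly different entry rules for earlier and later subjects. The planned sample size and interval width do not change.
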